**Health Economics/Outcomes Research
Methodological Protocol**

Drug Substance Nexium, LDA
Study Code D961FC00004

**A prospective descriptive, multi-national, multi-centre observational study
of burden of upper GI-symptoms in subjects with cardiovascular risk or
disease receiving treatment with low-dose aspirin**

Sponsor:

AstraZeneca R&D Molndal
[name]
Sweden

The following Amendment(s) and Administrative Changes have been made to this protocol:

Amendment Number	Date of Amendment	Local Amendment Number	Date of local Amendment
_____	_____	_____	_____
Administrative change Number.	Date of Administrative Change	Local Administrative change Number	Date of local Administrative Change

This submission /document contains trade secrets and confidential commercial information, disclosure of which is prohibited without providing advance notice to AstraZeneca and opportunity to object.

PROTOCOL SYNOPSIS

A prospective descriptive, multi-national, multi-centre observational study of burden of upper GI-symptoms in subjects with cardiovascular risk or disease receiving treatment with low-dose aspirin

Investigator

To be named.

Study centre(s), and number of subjects planned

Approximately 2000 subjects will be recruited from up to 80 centers in 3 countries (USA, Canada and France) and will be completing a one-time survey. Four hundred twenty (420) of these subjects will be followed for three months, with up to a maximum of 20 of these subjects undergoing personal interviews.

Study period

Estimated date of first subject enrolled

Estimated date of last subject completed

Objectives

The broad objective of this exploratory, observational, study is to characterize upper GI (Gastrointestinal) symptoms in subjects with Cardiovascular (CV) risk or confirmed disease taking low-dose aspirin (LDA) for primary or secondary CV disease prevention. More specifically, the study will:

- Characterize the frequency and nature of the upper GI symptoms
- Observe and record upper GI symptoms and compliance with LDA, and other relevant medications.
- Document the subject's behaviour, subjective experience, and evaluation of their condition (e.g., sleep, GI events, doctor's visits, etc.)

Study design

This is an observational study design delivering up to 15 months of data of which 12 months are retrospective and 3 months prospective. It consists of three stages: a one-time, cross-sectional survey; a prospective, three month diary; and, a personal (cognitive) interview. All data will be captured from subjects in the context of their usual care for CV disease, or risk for CV disease as ascertained by their physician, as such there will be no study treatment or intervention.

Target subject population

Females and males 18 years and above who have been prescribed low-dose aspirin (LDA) within the past 12 months, 75-325 mg, o-d owing to cardiovascular (CV) risk factor(s) and/or disease(s).

Outcome variables

Given the exploratory nature of the observational study a variety of outcome variables representing a number of domains will be measured. These will consist of demographics, medical and surgical history, with special attention to GI symptoms/diseases and concomitant medication. In addition, a variety of Patient Reported Outcomes (PRO) instruments will be utilized.

Patient Reported Outcomes (PROs)

PRO domains measured will include but not be limited to: GI symptoms, medication usage, medical history, healthcare utilization, daily activities, coping strategies, communication & relationship with their physician, sleep patterns and mood.

Health economics (not applicable)

Not applicable.

Statistical methods

A variety of statistical techniques appropriate for characterizing observational data and examining the study objectives will be applied. The complete analytic approach will be outlined in a separate Statistical Analysis Plan (SAP).

	PAGE
TITLE PAGE	1
PROTOCOL SYNOPSIS.....	2
TABLE OF CONTENTS.....	4
LIST OF ABBREVIATIONS AND DEFINITION OF TERMS	7
1. INTRODUCTION	9
1.1 Background	9
1.2 Rationale for this study	10
2. STUDY OBJECTIVES.....	10
3. STUDY PLAN AND PROCEDURES	10
3.1 Design and study flow synopsis.....	10
3.2 Rationale for study design	12
3.3 Selection of study population.....	12
3.3.1 Study selection record.....	12
3.3.2 Survey inclusion/exclusion criteria.....	13
3.3.2.1 Inclusion criteria	13
3.3.2.2 Exclusion criteria	13
3.3.3 Diary/EMA inclusion/exclusion criteria	14
3.3.3.1 Inclusion criteria	14
3.3.3.2 Exclusion criteria	14
3.3.4 Inclusion/Exclusion criteria – Cognitive interview	14
3.3.5 Restrictions	14
3.3.6 Discontinuation of subjects from assessment	15
3.3.6.1 Criteria for discontinuation	15

Ethics Committee	Synonymous to Institutional Review Board and Independent Ethics Committee
GCP	Good Clinical Practice
GI	Gastrointestinal
GSRS	Gastrointestinal Symptom Rating Scale
HE	Health Economics: Evaluations assessing and comparing the cost and consequences of different treatment options.
HRQL	Health Related Quality of Life: Multidimensional, subjective patient-reported outcomes.
ICH	International Conference on Harmonisation
International Co-ordinating investigator	If a study is conducted in several countries the International Co-ordinating Investigator is the Investigator co-ordinating the investigators and/or activities internationally.
IRB	Institutional Review Board
LDA	Low Dose Aspirin – referring to doses of 75-325 mg.
OR	Outcomes Research: The study of health related quality of life, health outcomes such as symptoms, sleep disturbances, physical functioning and subject or treatment satisfaction i.e., Patient-Reported Outcomes.
Outcome variable	A variable (usually a derived variable) specifically defined to be used in the analysis of a study objective.

Abbreviation or special term	Explanation
Parameter	A quantity (usually unknown) that characterizes the distribution of a variable in a population of subjects.
PDA	Personal Digital Assistant a small handheld electronic device that is used to capture and store information.
Principal Investigator	A person responsible for the conduct of a clinical study at an investigational study site. Every investigational study site has a Principal Investigator.
PRO	Patient-Reported Outcomes: Umbrella term categorising various types of subjective reported outcomes such as health-related quality of life, treatment satisfaction, subjective health status and subjective symptoms directly from the subject.
RDQ	Reflux Disease Questionnaire
SAP	Statistical Analysis Plan
SitePro	A PDA device that will be used to collect data electronically in the physicians office.
TS	Treatment Satisfaction: A comparison between perceived quality (good-poor) of a given treatment and the subject's initial expectations.
UGI	Upper Gastrointestinal
XQS	Extraesophageal Questionnaire Scores

1. INTRODUCTION

1.1 Background

For at least 2 decades low-dose acetylsalicylic acid (LDA) has been used for the prevention of thromboembolic events. The dose range of LDA is 75 to 325 mg daily. The individual doses for different indications vary between countries. The antithrombotic effect of LDA seems to be similar within the dose range of 75 to 325 mg daily (Patrono C et al 2005).

Continuous low-dose ASA treatment is accompanied by a variety of undesirable AEs. These include upper gastrointestinal (GI) symptoms such as dyspeptic symptoms, abdominal pain and/or heartburn (Silagy CA et al 1993, Laheij RFJ et al 2003), peptic ulcers which might be followed by serious ulcer complications such as bleeding, gastric or duodenal perforation and obstruction (Lanas A et al 2006, Yeomans ND et al 2005, García Rodríguez LA and Hernández-Díaz S 2004, CAPRIE Steering Committee 1996, Weil J et al 1995). Even taking ASA in doses as low as 75 mg daily significantly increases the risk of having symptomatic peptic ulcer as well as the risk of having upper GI bleeding compared with not taking aspirin (García Rodríguez LA and Hernández-Díaz S 2004, Weil J et al 1995, Laine L 2006).

While the risk, nature, and development of ulcer and ulcer complications associated with LDA treatment is well documented, less is known about upper GI symptoms. The nature, occurrence rate, and impact of upper GI symptoms associated with LDA treatment, as well as these symptoms' potential influence on compliance with LDA treatment, use of acid inhibitory drugs and other medications is the focus of the current study.

To understand how symptoms develop and are experienced, it is best to ask the subjects themselves (i.e. a patient reported outcome, PRO). Further it is important to understand these symptoms in a non-interventional, naturalistic environment. As such any methodology used needs to be aimed at observing, rather than influencing, the symptoms of interest. Historically, cross-sectional PRO surveys and face-to-face interviews have been used to evaluate subjects symptoms and disease experience. While useful for understanding the subjects' global perspective on their condition, retrospective recall is known to be problematic for documentation of the subjects' day-to-day experience.

To overcome the limitation of retrospective recall, real-time methods have been developed. Specifically, Ecological momentary assessment (EMA) is a method for gathering reliable data on subject events and experiences as they are occurring in real-time (Stone A et al 2003, Stone & Shiffman 2007). EMA methods have been successfully applied to gain understanding of how emerging disease processes and subject behaviour interact. Capturing real-time data from subjects using EMA methods yields a rich data stream that is then subject to statistical techniques that extract trends and offer potential links between behaviour and disease process. In settings such as the current one, where the GI symptom emergence and experience is not well understood, EMA methods are indicated.

1.2 Rationale for this study

Observing and documenting upper GI symptoms from a subject perspective will yield a better understanding of the nature of the symptoms (e.g., frequency, character, and how they emerge), the significance and impact of symptoms (e.g., impact on health related quality of life, and role in LDA non-compliance), and potentially point to ways of avoiding symptoms when these are a barrier to optimal CV risk management.

2. STUDY OBJECTIVES

The broad objective of this exploratory, observational, study is to characterize upper GI symptoms in subjects with CV risk or confirmed disease taking LDA for primary or secondary cardiovascular disease prevention. More specifically, the study will:

[figure not shown]
- Characterize the frequency and nature of the upper GI symptoms
- Observe and record upper GI symptoms and compliance with LDA, and other relevant medications.
- Document the subject's behaviour, subjective experience, and evaluation of their condition (e.g., sleep, GI events, doctor's visits, etc.).

3. STUDY PLAN AND PROCEDURES

3.1 Design and study flow synopsis

This is an observational study design delivering up to 15 months of data of which 12 months are retrospective and 3 months prospective. It consists of three stages: a one-time, cross-sectional survey; a prospective, three month diary; and, a personal (cognitive) interview. All data will be captured from subjects in the context of their usual care for CV disease or risk, that is, there will be no study treatment or intervention. Figure 1 is a graphical summary of the three stages.

Figure 1 **Flow Chart**

In the first stage of the study, approximately 2,000 subjects who have been prescribed LDA usage in the past 12 months, or those about to begin LDA, will complete a one-time in-office survey using an electronic personal digital assistant (PDA) device (termed SitePro). The survey will ask subjects about:

- Use of LDA (75-325 mg daily);
- subject’s experience, if any, of UGI symptoms during the time they were using LDA;
- the impact of UGI symptoms on the subject’s compliance with taking LDA and medications related to their CV disease or CV risk factors;
- background information about subject’s emotional state and well being.

The specific domains that will be assessed, and the actual items of the survey are listed in Section 4.2.1, and Appendix C. Additional information such as medical history and concomitant medications will be captured by the investigator using a paper CRF.

A subset of the subjects of whom all complete the survey will be invited to participate in a three (3) month prospective diary period where real-time assessments will be administered using the ecological momentary assessment (EMA) approach. Four hundred, twenty (420) subjects stratified into three groups varying on length of time using LDA will be asked to use

an electronic PRO device (ePRO) to record information about their experience with LDA for the period of 3 months. The ePRO device will prompt (via an audible alarm) the subject three (3) times each day and administer questions regarding the subject's experience with LDA. In particular, the ePRO device will ask subjects about UGI symptoms, medication use, and about their daily activities and mood. The areas of assessment are listed in Section 4.2.1 (Table 2), and the specific questions are listed in Appendix D. The goal is to obtain EMA data from 350 subjects in the three groups: 200 Naïve LDA users (240 enrolled) who begin LDA use at the time of the study; 100 Short-term LDA users (120 enrolled); and, 50 Long-term LDA users (60 enrolled). A detailed description of the inclusion/exclusion criteria for each EMA group can be found in Section 3.3.3.

Finally, a sample of up to 20 subjects from the three EMA groups will be interviewed (see Section 3.3.4) to further debrief their experience with LDA and upper GI symptoms. This 1 hour cognitive interview will include the following areas:

- the subject's experience with upper GI symptoms;
- the subject's use of and compliance with LDA and other CV related medication;
- the subject's perceived impact of upper GI symptoms on their ability to continue with medication;
- the broader impact of these symptoms on their life.

The subjects will be selected following review of Diary/EMA data, and investigators will be asked to invite selected subjects to participate in these interviews.

3.2 Rationale for study design

In order to gain a comprehensive view of upper GI symptoms in subjects with CV risk or disease on LDA, survey, interview, and EMA data will be captured from subjects. Such data will capture the natural history of the emergence and course of UGI symptoms in subjects taking LDA. Further, the impact of these symptoms on subject behaviour will also be recorded in a naturalistic, non-intervention setting. In sum, the design will allow the naturalistic study of the phenomena and will yield data that addresses the objectives of the study.

3.3 Selection of study population

3.3.1 Study selection record

Subjects will be identified through their primary care, cardiologist or practice group and asked to participate in the study. The investigative site will screen eligible subjects and inform them of the opportunity to participate in the study. Subjects 18 years of age and older, diagnosed as at risk or confirmed with CV disease, and who have been prescribed LDA in the past 12 months or are about to commence LDA will be asked to participate. Subjects interested and

qualified to participate will complete an informed consent and have questions answered by the investigator or site staff. Subjects meeting the inclusion/exclusion criteria for the survey will be asked to complete the survey on an SitePro device. Those completing the survey, and identified by the survey SitePro tool as potential EMA candidates, will be further reviewed for inclusion/exclusion into the Diary/EMA stage of the study. Subjects meeting the EMA inclusion/exclusion will be invited to participate in the EMA portion of the study. The specific inclusion/exclusion for each of these stages is delineated below.

3.3.2 Survey inclusion/exclusion criteria

3.3.2.1 Inclusion criteria

- Provision of signed written informed consent.
- Female or male aged 18 years and over.
- Physician prescribed or recommended daily intake of LDA (75-325 mg daily) for cardiovascular disease prevention within the past 12 months, including the day of entry into the study.
- Established cardiovascular disease, such as (but not restricted to) CAD (Coronary Artery Disease), previous TIA (Transient Ischemic Attack) or ischemic stroke (secondary prevention), or subjects with known risk factors for cardiovascular disease without having experienced cardiovascular events previously (primary prevention).
- In the judgement of the investigator, the subject is able to carry out the procedures required by the CSP.

3.3.2.2 Exclusion criteria

- Need for concomitant treatment with a non-ASA NSAID including a cyclooxygenase-2 (COX-2) selective NSAID. Occasional use of up to 1 day/week is allowed.
- Involvement in planning and conduct the study.
- Inability to read and understand how to complete electronic questionnaires.
- Hospitalised.
- Subjects with a history of alcohol or drug abuse that in the opinion of the investigator would contraindicate their participation in the study.

3.3.3 Diary/EMA inclusion/exclusion criteria

3.3.3.1 Inclusion criteria

In addition to the inclusion/exclusion for the survey, subjects will meet the following specific criteria for each of the EMA groups:

Group 1: “LDA Naïve Users”. These subjects will have been prescribed and will use LDA on the day they are invited to participate in the study. Subjects will not have reported any UGI symptoms in the past 14 days. One half (1/2) of the subjects in this group should have a history of having used a medication or remedy for upper GI symptoms in the past 12 months.

Group 2: “Short-term LDA Users”. These subjects will have been prescribed and having used LDA within a 14-day period of Visit 1, have reported one or more UGI symptoms during that 14-day period, and reported not having used any H2 blocker or PPI during the same period.

Group 3: “Long-term LDA Users”. These subjects will have been prescribed and having used LDA for at least 12 weeks and up to 12 months prior to Visit 1 or screening, have reported one or more UGI symptoms during the past 14-day period and having been prescribed or recommended a medication for acid suppression (H2 blockers or PPIs).

Subjects will be allocated to the groups according to their responses on the SitePro survey (see above), and the application of the inclusion/exclusion criteria by the investigative site.

3.3.3.2 Exclusion criteria

- Concomitant treatment with a non-ASA NSAID including a cyclooxygenase-2 (COX-2) selective NSAID. Occasional use of up to 1 day/week is allowed.
- Hospitalised at the time of the survey or EMA entry.
- Planned hospitalisation during the EMA data collection period (3 months).
- Inability to complete the diary daily.

3.3.4 Inclusion/Exclusion criteria – Cognitive interview

The inclusion of subjects into the cognitive interviewing will be based upon a review of the Diary/EMA data. The exact criteria will be determined in conjunction with AstraZeneca and depend upon the patterns of subject response emerging in the EMA reports during the study.

3.3.5 Restrictions

Not Applicable.

3.3.6 Discontinuation of subjects from assessment

3.3.6.1 Criteria for discontinuation

Subjects may be discontinued from study at any time. Specific reasons for discontinuing a subject from this study include:

1. Voluntary discontinuation by the subject who is free at any time to discontinue his/her participation in the study without prejudice to further treatment;
2. Severe non-compliance to the CSP as judged by the investigator and/or AstraZeneca;
3. Incorrect enrolment; i.e., enrolment in violation of the inclusion/exclusion criteria;
4. Subjects who are not completing at least 80% of their evening reports, indicating non-compliance with the diary recording requirements of the CSP;
5. If a physician recommends that the subject discontinue use of LDA, the subject will be discontinued from the study;
6. Intake of concomitant medication prohibited by the CSP.

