3.3.6.2 Procedures for discontinuation

Subjects who discontinue should always be asked about the reason(s) for their discontinuation. Any ePRO instruments should be returned by these subjects.

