3.3.7 Method of assigning subjects to study groups

Informed consent will be obtained before enrolment in the study and the subject identified with an enrolment number. Given the observational nature of the study, randomization into a treatment group will not occur. Placement into one of three EMA groups will take place using the SitePro device as described above (Section 3.3.3.1).

If a subject discontinues from the study, the subject number will not be reused, and the subject will not be allowed to re-enter the study.

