6.2.1 Cross-sectional survey data

Analysis of the data from the survey will primarily be descriptive statistics (e.g., measures of central tendency, correlation matrices) of the demographic characteristics of the sample, frequency of upper GI symptoms, and the nature of those symptoms. In addition, medication usage (amount, type duration of use etc.) will be assessed in relation to demographic, PRO instrument and upper GI related variables.

6.2.2 ePRO-Diary/EMA data

Data for the EMA subjects sub-sample will be examined following analytic techniques typically used in natural history studies (Stone & Shiffman 2007, Shiffman et al 1997). In such studies the same number of observations per subject is not expected. Rather, in natural history studies trends are analyzed utilizing General Estimating Equations (GEE; Zeger SL et al 1988), which allow for varying numbers of observations and take into account the clustering of data within subjects; allowing for the most appropriate autocorrelation structure for this type of data. The variables that will be entered into the GEE models will vary depending upon the specific study objective under evaluation. In general, there will be a focus on those variables related to the onset of upper GI symptoms, and those associated with change in LDA usage.

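### Criterion 5 ends the diary once a physician recommends stopping LDA, so the later course is never observed and loss of follow-up can depend on symptoms

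*Protocol*

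**What the plan says.** Criterion 5 in Section 3.3.6.1 states: "If a physician recommends that the subject discontinue use of LDA, the subject will be discontinued from the study". It is not limited to GI reasons or to permanent stops. The trigger is the recommendation itself, whether or not the subject acts on it. Section 3.3.6.2 then provides that "Subjects who discontinue should always be asked about the reason(s) for their discontinuation" and that "Any ePRO instruments should be returned by these subjects". Under Section 3.3.7, after discontinuation "the subject will not be allowed to re-enter the study". No section provides for diary entries beyond that point.

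Other sections set the aims. Section 3.1 says that there is no study treatment and that data come from usual care. Section 3.2 describes a naturalistic record of how symptoms emerge, run their course and affect behaviour. Section 1.2 names the symptoms' "role in LDA non-compliance" among the things to be understood, and Section 2 makes recording symptoms and LDA compliance an objective. For the diary analysis, Section 6.2.2 says "there will be a focus on those variables related to the onset of upper GI symptoms, and those associated with change in LDA usage". The method is GEE, chosen as models "which allow for varying numbers of observations and take into account the clustering of data within subjects".

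**The concern.** In a treatment trial, stopping the drug is sometimes used as the end of follow-up. Here there is no study drug, and a physician advising a subject to stop LDA is an event within the usual care that the study means to observe. The rule ends the diary at that event, which is one of the two routes by which LDA use can change. The other route, the subject skipping or stopping unprompted, is not a listed criterion and remains in the diary.

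Two things are at stake. First, nothing is known about what follows a physician-recommended stop: whether symptoms resolve, what other medication is taken, or whether LDA is resumed. Second, if the advice tends to follow symptoms, the subjects who leave are the more symptomatic ones, and those who remain look better over time. GEE copes with unequal numbers of observations, but without further adjustment it is generally unbiased only when the reason for leaving is unrelated to the outcome.

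**Working it through.** **1. The plan's own allowance for loss.** The current figures are in Amendment 2 (revised text of Section 3.1). Enrolled: 240 + 30 + 60 = 330. Expected to give data: 200 + 25 + 50 = 275. The ratio is the same in each group: 200/240 = 25/30 = 50/60 = 0.833, an implied loss of 1 − 0.833 = 16.7%. Check: 330 × 5/6 = 275. The figure reproduces, but it is one overall allowance and does not separate criterion 5 removals from other loss. Section 6.1 gives no formal sample size calculation, so there is no power figure to test.

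**2. The instrument against the rule.** The evening report in Appendix D asks whether low-dose aspirin, other heart medication or GI medication was taken. It also asks whether a doctor or hospital was visited and whether GI problems were the reason. The diary can therefore record a stop and its aftermath. Criterion 5, device return and the bar on re-entry switch it off. What remains is the diary up to that point, the fact of removal and the stated reason.

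**3. Illustration of the effect on symptom frequency.** The protocol gives no rate of stop recommendations and no link between them and symptoms, so all inputs here are assumptions:
- 90 days of follow-up.
- Each subject has a constant daily symptom probability, on the logit scale normal with mean −2 and SD 1.5, which averages about 19%.
- The daily hazard of a stop recommendation is h0 on a symptom-free day and h0 × HR on a symptom day.
- The subject leaves after the recommendation.
- Symptom probability does not change after the stop.

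The simulation used 200,000 subjects; removals are scaled to 330.

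| h0 per day | HR | Last-week frequency, all subjects | Last-week frequency, subjects remaining | Removed by day 90 | Person-days lost | Removed of 330 |
|---|---|---|---|---|---|---|
| 0.0005 | 1 | 0.189 | 0.189 | 4.4% | 2.2% | 14 |
| 0.0005 | 5 | 0.191 | 0.184 | 7.5% | 3.8% | 25 |
| 0.0002 | 20 | 0.190 | 0.179 | 7.7% | 3.9% | 25 |
| 0.0005 | 10 | 0.190 | 0.176 | 11.0% | 5.6% | 36 |
| 0.001 | 5 | 0.190 | 0.178 | 14.3% | 7.4% | 47 |
| 0.001 | 10 | 0.190 | 0.165 | 20.6% | 10.8% | 68 |

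When the advice is unrelated to symptoms (HR = 1) there is no distortion. When it is symptom-driven, a flat 19% appears as 16.5% to 18.4%: 0.190 − 0.184 = 0.6 points up to 0.190 − 0.165 = 2.5 points. The last row removes 20.6%, which exceeds the plan's whole 16.7% allowance if removed subjects count as lost, so it lies at the heavy end.

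**The case against.** The strongest reply is that little is lost. A physician-recommended stop is itself a recorded event with a reason, and the diary before it is kept, so the stop can be analysed as an outcome with its preceding symptoms. That stands: only the course afterwards is missing.

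A reader might infer more, namely that the association between symptoms and stopping LDA is biased toward zero. Take, as an assumption, stops in 20 of 100 symptomatic and 5 of 100 asymptomatic subjects, 60% of them physician-recommended. Keeping removed subjects in the denominator gives 8% against 2%, so the 15-point difference seems to shrink to 6. But removed subjects are not there to be counted as non-stoppers. Without them:
- The proportions are 8/(8 + 80) = 9.1% and 2/(2 + 95) = 2.1%, a difference of about 7 points.
- The odds ratio is (20 × 95)/(80 × 5) = 4.75 before and (8 × 95)/(80 × 2) = 4.75 after.
- The risk ratio rises from 4.0 to 4.4.

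More generally, the odds ratio is multiplied by (1 − f1)/(1 − f0), where f1 and f0 are the physician-recommended shares of stops in symptomatic and asymptomatic subjects. The direction depends on shares that the protocol does not give. If recorded removals are counted as stops, 20% against 5% is recovered. A general bias toward zero is not supported.

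Other replies carry partial weight:
- Following medical advice to stop is not non-compliance, so Sections 1.2 and 2 bear on this only loosely. The wider wording on LDA usage in Section 6.2.2 does cover it.
- The Appendix C survey asks whether aspirin was stopped because of GI symptoms. That is recall, not the daily course.
- Ending follow-up at the stop is coherent for symptoms while taking LDA. However, an on-LDA summary can be made from a continued diary, whereas the reverse is impossible.
- Section 6.2.2 does not say that the GEE will be unweighted, and the SAP, not shown, may provide weighting based on recorded symptoms. Weighting cannot supply observations that were never collected.

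A reader might also extend the point to criterion 6 ("Intake of concomitant medication prohibited by the CSP"). The documents do not support that: NSAID use beyond one day a week is an eligibility exclusion (Sections 3.3.2.2 and 3.3.3.2), and nothing shows that such removals depend on symptoms.

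**Conclusion.** The point holds for criterion 5 in a limited form. The rule conflicts with the non-interventional, naturalistic design in Sections 3.1 and 3.2 and with the focus on LDA usage in Section 6.2.2. Its certain cost is that symptoms, medication use and any LDA restart after a physician-recommended stop are never observed. Its conditional cost is informative loss of follow-up, to the extent that the advice follows symptoms. The study's own premise makes that plausible, but the protocol does not quantify it.

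The 0.6 to 2.5 points rest entirely on assumed hazards, on hazard ratios of 5 to 20 and on symptoms unchanged by stopping. If symptoms ease after a stop, an all-days frequency would truly fall, and only continued observation could show it. The study is exploratory and tests no hypotheses, so this is a worthwhile and cheap correction; it does not invalidate the diary stage.

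**What to change.** Reconcile criterion 5 with Sections 3.2 and 6.2.2 by separating an LDA stop from the end of assessment. For EMA subjects:
- Continue the diary to Visit 3 after a physician-recommended stop.
- Record the date, initiator and reason of every LDA stop.
- Analyse physician-initiated and subject-initiated stops as outcomes.
- Report symptom frequency over all days, and also split into on-LDA and post-stop days. State that the on-LDA summary remains subject to depletion of symptomatic subjects, because continuing the diary does not cure that part.

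The cost is a wording amendment, plus some subjects keeping a device they already hold for the rest of the 90 days. The physician's decision on LDA is unaffected, and criterion 6 can stay as it is.
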